### 1.3 Conventional imaging is inadequate to differentiate high grade gliomas and normal tissue

Image-guided techniques have assumed a central role in maximizing the therapeutic benefit of first-line multi-modal treatment for gliomas. However there are significant deficiencies associated with conventional contrast enhanced magnetic resonance imaging, the current standard of care for image-guided radiotherapy (RT) of brain tumors. MRI findings typically include a heterogeneous area of CE solid tumor surrounded by a large area of vasogenic edema. Contrast enhancement on T1-weighted images is used to identify regions of highest tumor density/grade or malignant potential for radiotherapy planning. However, approximately one-third of high-grade gliomas demonstrate no contrast enhancement. Although used to define the extent of tumor infiltration relative to normal neuro-anatomic structures, abnormal T2/FLAIR signal is known to contain both regions of nontumoral vasogenic edema and non-uniform tumor infiltration. Recent spectroscopic data suggest that the infiltration of tumor cells is not necessarily uniform with some areas of T2 change more likely to be edema and other areas more likely to have tumor infiltration. Furthermore, tumor infiltration has been found to extend beyond areas that demonstrate abnormal T2/FLAIR or enhancement. There is a critical need to incorporate imaging-based techniques to guide therapy that address these deficiencies of MRI imaging. Molecular imaging techniques provide visual information about biological processes and have the potential to improve the accuracy of RT tumor delineation, which impact the overall course of treatment and prognosis for brain tumor patients.

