## **1.7 Advanced MRI techniques**

Advanced techniques using perfusion MRI(pMRI) and diffusion tensor imaging (DTI) also show promise for better differentiation of high density tumor and post-treatment radiation effect from true tumor progression compared to CE-MRI. No reported studies have performed a head-to-head comparison of F-DOPA-PET with pMRI and DTI. [name] has extensive experience with the use of state-of-the-art MR for gliomas, and has demonstrated the direct impact of both acquisition and post-processing on determining relative cerebral blood volume (relCBV) threshold values for distinguishing tumor from post-treatment radiation effect. Differences in RT volumes identified using biopsy-validated thresholds as highly aggressive disease comparing F-DOPA uptake and relCBV from pMRI as well as differences in RT volumes identified using biopsy-validated thresholds as tumor extent comparing F-DOPA uptake and diffusion maps from DTI will be evaluated.

In summary, F-DOPA-PET metabolic imaging demonstrates significant correlation with histopathologic markers of grade and cellularity. MC1374 suggests that biopsy-validated F-DOPA-PET thresholds may reliably delineate areas of high-grade glioma not otherwise recognized with standard MRI. MC1374 suggest that F-DOPA-PET may more accurately identify regions of higher grade disease in patients with glioma and will have utility in guiding radiotherapy targeting. Future incorporation of F-DOPA-PET into clinical practice for radiation therapy planning will evaluate the influence of F-DOPA-PET on local control and survival outcomes.

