### **2.3 Correlative Research**

2.3.1 Compare RT treatment volumes defined by MR only with RT treatment volumes defined with both PET and MR information for Grade IV glioma patients.

2.3.2 Compare differences in RT volumes identified using biopsy-validated thresholds as highly aggressive disease comparing 18F-DOPA uptake and relCBV from pMRI as well as differences

in RT volumes identified using biopsy-validated thresholds as tumor extent comparing F-DOPA uptake and diffusion maps from DTI will be evaluated.

2.3.3 Evaluate quality of life after radiotherapy using EORTC questionnaires compared with historical controls from Keim-Guibert et al.

2.3.4 Compare differences in proton radiation planning utilizing radiobiologic modeling/evaluation techniques performed at Mayo Clinic Rochester to Linear Energy Transfer distribution evaluation at Mayo Clinic Arizona

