#### 16.2.2 Sample Size

The one-stage design to be utilized is fully described in Section 16.22. A minimum of 39 evaluable patients will be accrued to this phase-II study unless undue toxicity is encountered. We anticipate accruing an additional 4 patients to account for ineligibility, cancellation, major treatment violation, or other reasons. Maximum projected accrual is therefore 43 patients.

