### 16.4 Correlative Research

16.4.1 Compare RT treatment volumes defined by MR only with RT treatment volumes defined with both PET and MR information. To assess the impact of integrating PET on target definition, the treating radiation oncologists will first define the treatment volumes for CTVMR and using the MR images while blinded to the PET study. Then the PET study will be reviewed with the planning CT and MRI studies to allow contouring of the CTVPET defined by the T/N ratio of >2.0, respectively. The contours will be combined by the treating radiation oncologist and then expanded as described above. The volume of overlap and non-overlap between the CTV defined by MR and that defined by PET will be calculated. Similarly, the MR-only defined volumes will be compared against the volumes defined with the combination of MR and PET planning. Paired t-test statistical analysis will be performed to determine if any differences exist and the level of statistical significance between treatment volumes defined by MR only and treatment volumes

defined with both PET and MR information. Alternate metrics for comparison will also be assessed, including spatial overlap, distance, correlations and 3D shape comparisons.

16.4.2 Compare differences in RT volumes identified using biopsy-validated thresholds as highly aggressive disease comparing F-DOPA uptake and relCBV from pMRI as well as differences in RT volumes identified using biopsy-validated thresholds as tumor extent comparing F-DOPA uptake and diffusion maps from DTI will be evaluated. Paired t-test statistical analysis will be performed to determine if any differences exist and the level of statistical significance between RT volumes based on F-DOPA uptake and the measures mentioned above.

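### Section 16.4.2 compares 18F-DOPA with perfusion and diffusion MRI by volume alone, so regions of similar average size in different places would show no difference

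*Combined protocol and SAP*

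**What the plan says.** Objective 2.3.2 is to "Compare differences in RT volumes identified using biopsy-validated thresholds as highly aggressive disease" between 18F-DOPA uptake and relCBV from perfusion MRI, and to make the corresponding comparison of tumor extent between 18F-DOPA uptake and DTI diffusion maps. Section 1.7 gives the motivation: "No reported studies have performed a head-to-head comparison of" DOPA-PET with these two MRI techniques. It goes on to anticipate a role for DOPA-PET in guiding radiotherapy targeting.

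Section 16.4.2 restates the objective and then names one analysis: "Paired t-test statistical analysis will be performed to determine if any differences exist and the level of statistical significance between RT volumes based on" 18F-DOPA uptake and the MRI measures. No other metric, margin, significance level or sample size is attached to it.

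Section 16.4.1, immediately before, covers a different comparison: MR-only volumes against volumes defined with PET and MR together. It also uses a paired t-test, but adds spatial measures. First, "The volume of overlap and non-overlap between the CTV defined by MR and that defined by PET will be calculated". Then, after its t-test, "Alternate metrics for comparison will also be assessed, including spatial overlap, distance, correlations and 3D shape comparisons". Section 16.4.2 neither repeats these measures nor refers back to them.

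**The concern.** A paired t-test on volume reduces each method to one number per patient, its size in cc. Where the region lies does not enter. For a comparison that is meant to inform targeting, location matters as well as size, and the protocol's own background is spatial. Section 1.3 says the infiltration of "tumor cells is not necessarily uniform with some areas of T2 change more likely to be edema", while other areas are more likely to contain infiltrating tumor.

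Two outcomes would be hard to interpret. A non-significant result is compatible with full overlap, partial overlap or none. A significant result says that one method marks more tissue on average, but not whether the larger region contains the smaller. Because the test concerns the mean difference, size differences in opposite directions in different patients can also cancel. What is at stake is how informative a comparison described as not previously reported can be.

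**Working it through.** The plan gives no power, significance level or expected difference for 16.4.2, so there is no stated figure to reproduce. The check has three parts.

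**1. What the test can see.** For one patient let A be the DOPA region and B the MRI region. Then

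- DOPA-only volume = |A| − |A∩B|
- MRI-only volume = |B| − |A∩B|
- volume difference = |A| − |B| = DOPA-only − MRI-only

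The overlap |A∩B| cancels. The paired t statistic, mean(|A| − |B|) / (SD(|A| − |B|)/√n), therefore does not depend on it. The test asks only whether the two non-shared parts are equal on average, not whether they are small.

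**2. Size of the blind spot in one patient.** Assumption: two equal spheres of 30 cc. The documents give no volume for these regions.

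- Radius r = (3 × 30 / 4π)^(1/3) = 1.93 cm, so 2r = 3.86 cm.
- For equal spheres with centres d apart, Dice = 1 − 1.5(d/2r) + 0.5(d/2r)³, and Dice = 0 once d ≥ 2r.
- At d = 2.0 cm, d/2r = 0.518, so Dice = 1 − 0.777 + 0.070 = 0.29.
- Shared volume = 0.29 × 30 = 8.7 cc. DOPA-only = MRI-only = 30 − 8.7 = 21.3 cc. Volume difference = 21.3 − 21.3 = 0 cc.
- At d = 39 mm or more, Dice = 0 and the volume difference is still 0 cc.

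**3. Behaviour of the test across a trial.** Assumptions, none from the documents: two-sided 0.05, median volume 40 cc, between-patient log-SD 0.6, within-method log-SD 0.2, 4,000 simulated trials per setting. The number of pairs is taken as 20, 39 or 43. Section 16.2.2 says "A minimum of 39 evaluable patients will be accrued to this phase-II study unless undue toxicity is encountered" and projects at most 43. The smaller value allows for advanced MRI being discretionary at Rochester (section 4.0, footnote 9, and section 7.1.6).

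| Setting | Trials with p < 0.05 |
|---|---|
| Equal expected volumes, n = 20, 39 or 43 | about 4 to 5% |
| One method 10% larger, n = 39 | about 40% |
| One method 20% larger, n = 39 | about 91% |
| One method 30% larger, n = 39 | over 99% |

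The first row is the nominal error rate. It applies equally to 40 cc spheres that coincide (Dice 1.00), have centres one radius apart (Dice 1 − 0.75 + 0.0625 = 0.31) or are disjoint (Dice 0). This holds by construction, because location is not an input. The remaining rows show that the test responds to size, and does so wherever the regions lie.

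**The case against.** The strongest reply is that the objective, in 2.3.2 and again in 16.4.2, speaks of differences in RT volumes. A paired comparison of volumes is a literal, if narrow, answer. That stands. A reader might infer that the objective asks whether the methods find the same disease or are interchangeable, but the documents state no such question.

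A second reply is that the sentence on alternate metrics in 16.4.1 was meant to cover 16.4.2 too. That may have been the intention. However, the sentence closes the comparison of MR-only with PET+MR volumes, and 16.4.2 then states its own analysis without a cross-reference. As written, it does not reach 16.4.2.

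A reader might also infer that the protocol overlooks location altogether, or measures overlap only where one volume contains the other. It does neither. Section 16.4.1 plans overlap and non-overlap between the MR-defined CTV and the PET-defined CTV, which are not nested. The gap is a method not carried forward one paragraph.

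It is tempting to take the 3.5 cm figure in section 1.5 as evidence that displacements of 20 to 39 mm are likely. It does not show that. It is a maximum extension of DOPA uptake beyond T1 contrast enhancement, not a centre-to-centre shift, and it does not involve relCBV or diffusion maps. Extension outward would also tend to enlarge the PET volume, which a volume test can detect. The documents give no spatial figure for DOPA against either MRI measure.

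**Conclusion.** The point holds as a cheap improvement. Section 16.4.2 names no spatial metric, and the test it does name cannot distinguish coincident from disjoint regions of similar average size. The illustration (Dice about 0.29 at 20 mm, 0 at 39 mm or more, with a volume difference of 0 cc throughout) rests on assumed equal 30 cc spheres. It shows what the test can miss, not how often that would happen in these patients.

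Two stronger readings should be resisted. One is that methods marking different places would always be reported as not different. That outcome is to be expected only when mean sizes are also similar: under the simulation's assumptions, a 20% size difference would be found in about 91% of trials at n = 39. The other is that the trial plans to treat non-significance as agreement, or to replace PET with perfusion or diffusion MRI. No section says so, and no decision rule is attached. The objective is correlative, and the primary endpoint is unaffected.

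**What to change.** Extend the spatial metrics of 16.4.1 to each pair in 16.4.2 (DOPA versus relCBV; DOPA versus diffusion). For each patient report:

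- Dice = 2|A∩B| / (|A| + |B|);
- DOPA-only and MRI-only volumes in cc;
- a surface distance between the two regions.

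Summarise each across patients with a confidence interval, alongside the paired t-test, which can stay. State the number of patients contributing to each pair, and say in advance how a patient is handled when one method marks no region, since surface distance is then undefined. Add one sentence that a non-significant volume difference is not evidence of spatial agreement. Settling this before analysis also avoids choosing metrics after seeing the data.

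The cost is a short amendment to the analysis text and some extra work. Section 7.1.9 already co-registers CT, MRI and PET to define the CTVs, but it does not say that the relCBV and DTI threshold volumes are registered to the PET, so that step may need adding. The metrics will exist only for patients who had advanced MRI, which is discretionary at Rochester. No additional patients are needed.

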#### 16.4.3 Quality of Life

Evaluate quality of life after radiotherapy treatment targeting dose escalated volumes defined to include high F-DOPA-PET uptake. QOL surveys will be compared to data from historical controls. Quality of life will be assessed at baseline and at each MRI evaluation (up to 6 evaluations). QOL will be measured using the EORTC QLQ-C30, a 30-item patient-reported questionnaire about patient ability to function, symptoms related to the cancer and its treatment, overall health and quality of life, and perceived financial impact of the cancer and its treatment. 28 of the 30 items are measured on a 1-4 scale (1=not at all; 4=very much) with the remaining two items (overall health and overall quality of life) scored on a 1-7 numeric analogue scale (1=very poor; 7=excellent). The recall period for the EORTC QLQ-C30 is one week. The EORTC QLQ-C30 is the product of more than a decade of collaborative research and to date, more than 2200 studies using the EORTC QLQ-C30 have been registered with the EORTC (Fayers et al, 2001 [EORTC Scoring Manual]). Of the 30 items, 24 aggregate into nine multi-item scales representing various HRQoL dimensions: five functioning scales (physical, role, emotional, cognitive and social), three symptom scales (fatigue, pain and nausea), and one global measure of health status. The remaining six single-item scales assess symptoms: dyspnea, appetite loss, sleep disturbance, constipation and diarrhea, and the perceived financial impact of the disease treatment. High scores indicate better QoL for the global health status and functioning scales, and worse QoL for the symptom scales. The QLQ-BN20 contains 20 items, 13 of which aggregate into four scales assessing future uncertainty, visual disorder, motor dysfunction, and communication deficit. The remaining single items assess other disease symptoms (e.g. headaches and seizures) and treatment toxic effects (e.g. hair loss) For all these scales, a higher score represents worse QOL.

The patient-completed questionnaires will be administered to all willing patients via paper or electronic format in clinic at baseline and at each evaluation. Questionnaires will be scored according to the published scoring algorithms.

Scale score trajectories over time will be examined using stream plots and mean plots with standard deviation error bars overall. Analysis will include change from baseline using t-tests and mixed linear models to test for changes at each time point and non-zero slope respectfully.

16.4.4 Compare differences in proton radiation planning utilizing radiobiologic modeling/evaluation techniques performed at Mayo Clinic Rochester to Linear Energy Transfer (LET) distribution evaluation at Mayo Clinic Arizona. Paired t-test statistical analysis will be performed to determine if any differences exist and the level of statistical

significance between proton plan metrics based off the two modeling/evaluation techniques.

## 16.5 Data and Safety Monitoring Plan

16.5.1 The Study Chairs and the study statistician will review the study at least twice a year to identify accrual, adverse event, and any endpoint problems that might be developing. The Mayo Clinic Cancer Center (MCCC) Data Safety and Monitoring Board (DSMB) is responsible for reviewing the accrual and safety for this trial at least twice a year, based on reports provided by the MCCC Statistical Office.

### 16.5.2 Adverse Event Stopping Rules:

As no reactions to F-DOPA have been reported within Mayo Clinic Rochester, toxicity testing reported in the literature revealed no deleterious effects (section 15.0), no reactions are anticipated. As such, at any point in the enrollment process after 10 or more patients have been enrolled, if more than 10% of these patients enrolled are unable to complete PET scanning due to allergic reactions to the tracer, enrollment will be suspended so that details of each episode can be examined and a trial recommendation will be formulated and presented to the MCCC DSMB. There have been no reports in the literature of the occurrence of NSF in patients with normal renal function. Additionally, we will use the contrast agent gadobenate dimeglumine, which has been shown to have a high safety profile (lower incidence of NSF in patients with renal failure/insufficiency) compared with many other available Gd-based contrast agents. Therefore no reactions are anticipated. As such, if at any time a patient develops NSF enrollment will be suspended so that details of the episode can be examined and a trial recommendation will be formulated and presented to the MCCC DSMB.

Using the hypofractionation approach described in Section 7, previous studies have successfully used hypofractionation without significant increases in acute or late adverse effects. However, some studies with more aggressive, higher daily doses of hypofractionation have reported increased toxicity. Nonetheless, both acute (available at <http://ctep.cancer.gov>) and late toxicity will be monitored continuously as each patient is accrued and follow-up data are accumulated. As such, at any point in the enrollment process after 10 or more patients have been enrolled, if more than 10% of these patients enrolled experience any of the following adverse events *considered to be at least possibly related to treatment*, enrollment will be suspended so the details of each episode can be examined and a trial recommendation will be formulated and presented to the DSMB

- Grade 3 or 4 irreversible CNS toxicity
- Grade 4 non-hematologic, non-CNS toxicity
- Any Grade 5 toxicity

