### 16.2.3 Accrual Time and Study Duration

We anticipate enrolling 15-20 patients per year and thus plan to finish accrual of patients by year 2, leaving year 3 for follow-up and analysis. Therefore, the overall study duration is expected to be 36 months.

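### The automatic treatment-toxicity rule in section 16.5.2 waits for ten enrolled patients, although two affected patients already known among the first nine make suspension at patient 10 certain

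*Combined protocol and SAP*

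**What the plan says.** Section 16.5.2 sets the treatment-toxicity rule. It applies "at any point in the enrollment process after 10 or more patients have been enrolled" and acts "if more than 10% of these patients enrolled experience any of the following adverse events", provided the events are at least possibly related to treatment. The list covers irreversible Grade 3 or 4 CNS toxicity, Grade 4 non-hematologic non-CNS toxicity, and "Any Grade 5 toxicity". The consequence is that "enrollment will be suspended so the details of each episode can be examined", followed by a recommendation to the DSMB. The tracer-allergy rule in the same section has the same ten-patient start; this point concerns the toxicity rule.

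The NSF rule in that section has no waiting period: "if at any time a patient develops NSF enrollment will be suspended".

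Other oversight is in place from the start:
- Section 16.5.2 says that "toxicity will be monitored continuously as each patient is accrued and follow-up data are accumulated".
- Under section 16.5.1 the study chairs and statistician review the study at least twice a year, and the DSMB "is responsible for reviewing the accrual and safety for this trial at least twice a year".
- Section 16.2.2 makes accrual conditional on the absence of undue toxicity, and section 16.2.5 lets adverse events weigh in a decision to terminate.
- Sections 10.4 and 10.5.2 set expedited reporting, including 24-hour reporting of any death within 30 days of the last radiation dose.

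On accrual, section 16.2.3 states: "We anticipate enrolling 15-20 patients per year". Section 16.2.2 caps accrual at 43.

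**The concern.** A minimum denominator is normally there to stop a percentage rule from firing on one early event: 1/9 is 11%, which would exceed the threshold. Here it also holds back the rule when two patients are affected, where it protects nothing. Two affected patients is exactly what the rule requires at ten enrolled, so from the moment the second is known the suspension is determined and only its date is open.

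The wait covers the start of the trial, when least is known about the regimen: ten patients take 10/20 × 12 = 6 months to 10/15 × 12 = 8 months. It also covers the gravest category. Two deaths at least possibly related to treatment among the first nine patients would not trigger the automatic rule. At stake are the patients who may be enrolled between the second known case and the tenth enrolment.

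**Working it through.** The documents give no suspension probability or expected exposure for this rule, so there is no figure to reproduce. They also give no true rate of qualifying toxicity for this regimen; 5% to 30% is an assumed range.

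**1. The boundary.** The trigger at n enrolled is the smallest x with x/n > 0.10.
- n = 10: 1/10 = 10.0% does not trigger; 2/10 = 20% does.
- n = 11, if the rule is read as starting after the tenth patient: 2/11 = 18.2% triggers.
- In full: 2 patients for n = 10–19, 3 for 20–29, 4 for 30–39, 5 for 40–43.

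Two patients known to be affected before patient 10 are still at least two at patient 10, so the trigger is certain.

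**2. Events known at once.** Let p be the true rate.
- Chance of at least two affected among the first nine: P = 1 − (1−p)^9 − 9p(1−p)^8. At p = 0.10: 1 − 0.3874 − 0.3874 = 0.225.
- If the second affected patient is number k (2 to 9), then 10 − k further patients, between 1 and 8, are enrolled before the rule acts.
- Mean spared per trial: E = Σ (k−1)p²(1−p)^(k−2)(10−k), over k = 2 to 9. The mean when an early double event occurs is E/P.

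| True rate (assumed) | P | Mean spared, all trials | Mean spared, given an early double event |
|---|---|---|---|
| 5% | 7.1% | 0.25 | 3.5 |
| 10% | 22.5% | 0.85 | 3.8 |
| 20% | 56.4% | 2.4 | 4.3 |
| 30% | 80.4% | 3.9 | 4.9 |

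**3. Events known after a delay.** Take even accrual at 17.5 per year, the middle of the stated range, so one patient every 12/17.5 = 0.686 months.
- Three-month fixed delay: 3/0.686 = 4.4 intervals, so only events in patients 1 to 5 are known before patient 10 enrols. P(at least 2 of 5) = 2.3%, 8.1%, 26.3% and 47.2% at the four rates. The second case, in patient k, becomes known with k + 4 enrolled, so 6 − k are spared. At p = 0.10 the mean per trial is 0.01 × 4 + 0.018 × 3 + 0.0243 × 2 + 0.02916 × 1 = 0.17.
- The accrual range matters. Under the same three-month delay, six patients are informative at 15 per year and four at 20 per year, giving 5–11% at a 10% rate and 18–34% at a 20% rate.
- Six-month fixed delay: 6/0.686 = 8.75 intervals, so only patient 1 is informative and an early double event cannot be known in time. At 15 per year two patients are informative, giving p² = 1% at a 10% rate and 4% at 20%.

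**4. Effect on overall suspension.** The rule as written was compared with the same rule active from the second affected patient, in 200,000 simulated sequences of 43 patients per rate, with events known at once. The chance of ever suspending was identical: 0.30, 0.72, 0.98 and above 0.99. Mean enrolled at suspension (43 if never suspended), as written against changed: 35.0 and 34.8; 23.7 and 22.8; 13.0 and 10.6; 10.6 and 6.7. The equality is logical, not a simulation result, because every early crossing is also a crossing at patient 10.

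**The case against.** The best defence is that the plan neither contradicts itself nor miscalculates here, that a minimum denominator has a purpose, and that patients 1 to 9 are not unprotected. That last part stands. A reader might infer that no safety rule operates for the first six to eight months; the documents do not support this. The NSF rule acts at any time, toxicity is monitored continuously, reviews occur at least twice a year, and deaths soon after radiation are reported within 24 hours. The chairs or the DSMB could suspend earlier at discretion. Hence enrolment may continue, not must continue. What remains is that none of these provisions sets a threshold or requires suspension for two affected patients. Expedited reporting also has gaps: section 10.4.2 exempts CNS necrosis up to Grade 3, although irreversible Grade 3 CNS toxicity counts towards the rule.

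A reader might also infer that the trial's outcome is settled by the second case. Crossing the threshold suspends enrolment pending review; it does not end the trial.

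The objection on size also stands. The 3.5 to 4.9 patients are conditional on an early double event and on immediate knowledge. The average over all trials is smaller, and irreversible CNS toxicity takes time to establish. If two cases surface only when 20 are enrolled, 2/20 = 10% does not trigger at all.

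Finally, the comparison with NSF shows only that the section can act without a waiting period. It does not show that a single toxicity event ought to suspend enrolment.

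**Conclusion.** The point holds in limited form. The automatic toxicity rule is inactive for the first nine patients even when its trigger at patient 10 is already certain, and no other provision requires suspension in that situation. The wait does serve to avoid suspending on one early event, but a requirement of two affected patients does that equally well.

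The benefit of closing the gap ranges from negligible to a few patients per trial. With immediate knowledge it averages 0.25 at a 5% true rate to 3.9 at 30%; with a three-month delay it is about 0.2 at a 10% rate; with six months it is close to nil. It is mainly a gain for acute toxicity. These sizes rest on assumed rates, independent patients, even accrual within the stated range, and fixed delays. The certainty of the trigger rests on none of these. It requires only that two different patients are known to be affected, with attribution made, before patient 10 enrols, and that enrolment reaches ten.

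**What to change.** In section 16.5.2, state the existing more-than-10% threshold as numbers of affected patients, active from the first enrolment: suspend enrolment for review when 2 patients are affected with fewer than 20 enrolled, 3 with 20–29, 4 with 30–39, and 5 with 40–43. Say explicitly that the count is of patients and not of events, since two events in one patient do not meet the present rule.

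The cost is protocol wording only. From ten patients onward the threshold is unchanged. Below ten, one affected patient still does not suspend. No suspension is added; some come earlier. Immediate referral of a single related Grade 5 event would be a separate and stricter rule and is not part of this change.

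### Section 16.5.2 counts a treatment-related death only within a pooled more-than-10% limit, so one or more such deaths need not suspend enrolment

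*Combined protocol and SAP*

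**What the plan says.** Section 16.5.2 of the combined protocol and SAP holds three suspension rules. In each, enrolment is suspended, the episodes are examined and a recommendation goes to the DSMB.

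- **Toxicity rule.** It applies "at any point in the enrollment process after 10 or more patients have been enrolled" and is met "if more than 10% of these patients enrolled experience any of the following adverse events". The events must be "considered to be at least possibly related to treatment". The list is "Grade 3 or 4 irreversible CNS toxicity", "Grade 4 non-hematologic, non-CNS toxicity" and "Any Grade 5 toxicity". Deaths have no limit of their own.
- **NSF rule.** One case is enough: "if at any time a patient develops NSF enrollment will be suspended".
- **Tracer rule.** It uses the same 10-patient start and 10% limit, but counts only patients who "are unable to complete PET scanning due to allergic reactions to the tracer".

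Other sections bear on deaths without suspending enrolment. Section 10.5.2 requires a 24-hour report of any death within 1 day of the tracer or 30 days of the last radiation dose, and of later deaths with at least possible attribution. Section 16.5.1 has the study chairs and the DSMB review the trial at least twice a year. Section 16.2.2 makes accrual conditional on the absence of undue toxicity, and Section 16.2.5 lets adverse events inform a decision to terminate. The maximum accrual is 43 (Section 16.2.2).

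**The concern.** Under the toxicity rule a death judged possibly caused by treatment weighs no more than an irreversible Grade 3 CNS event, and by itself it never reaches the limit. Before the tenth enrolment the rule does not operate at all. The same section already contains a one-event, any-time trigger, but reserves it for a reaction that it does not anticipate.

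What is at stake is the automatic safeguard. Without it, enrolment after a related death continues unless someone chooses to pause it. At the 15-20 patients per year of Section 16.2.3, a half-yearly review interval spans about 8 to 10 enrolments (15/2 = 7.5; 20/2 = 10). Section 1.1 reports radiation necrosis in 50% and in 20 of 46 patients in two hypofractionated series, and Section 16.5.2 itself accepts that more aggressive regimens have shown increased toxicity.

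The tracer rule has a related gap. A reaction first noticed at the assessment made after the scan (Section 10.6.1) has not prevented the scan, so it is not counted.

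**Working it through.** The plan states no operating characteristics for the toxicity rule, so there is no figure of its own to reproduce.

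**Step 1: boundary.** Inputs from Sections 16.5.2 and 16.2.2: strictly more than 10%, from n = 10, up to n = 43. The largest count x that does not suspend satisfies x/n ≤ 0.10.

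| Enrolled (n) | Largest count without suspension | Count that suspends |
|---|---|---|
| fewer than 10 | rule not in force | none |
| 10-19 | 1 | 2 (2/19 = 10.5%) |
| 20-29 | 2 (2/20 = 10.0%) | 3 (3/29 = 10.3%) |
| 30-39 | 3 (3/30 = 10.0%) | 4 (4/39 = 10.3%) |
| 40-43 | 4 (4/40 = 10.0%; 4/43 = 9.3%) | 5 (5/43 = 11.6%) |

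Events among the first 9 patients do enter the count once the tenth is enrolled. For NSF the count that suspends is 1 at any n.

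**Step 2: deaths only.** The documents give no treatment-related death rate, so p is an assumption. Each patient has a related death with probability p, known at once. The running count is checked after every patient from n = 10 to 43 by exact binomial recursion, and paths that exceed n/10 are removed as suspended. Suspension needs at least two deaths, so

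P(at least 1 death, never suspended) = [1 − (1 − p)^43] − P(suspended).

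| Assumed p | P(at least 1 death by 43) | P(suspended) | At least 1, never suspended | At least 2, never suspended | 4, never suspended |
|---|---|---|---|---|---|
| 3% | 0.73 | 0.13 | 0.60 | 0.24 | 0.005 |
| 5% | 0.89 | 0.30 | 0.59 | 0.34 | 0.016 |

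**Step 3: the pooled count as written.** Now let other listed events occur in 5% of patients (a further assumption), independently of death, with each patient counted once. The same recursion gives:

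| Assumed p | At least 1 death, never suspended | At least 2 deaths, never suspended |
|---|---|---|
| 3% | 0.25 | 0.08 |
| 5% | 0.22 | 0.10 |

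**Step 4: a one-death trigger.** It fires at least once by patient 43 with probability 1 − (1 − p)^43, which is 0.58, 0.73 and 0.89 at p = 2%, 3% and 5%. The expected number of pauses is 43p: 0.86, 1.29 and 2.15.

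**Step 5: tracer rule, by reading.** Section 8.0 takes a patient who reacts during injection off study without PET, so that reaction is counted. A reaction found after a completed scan is recorded (Sections 4.0 and 10.6.1) but not counted by the tracer rule. Section 10.4.2 exempts allergic reactions up to Grade 3 from expedited reporting, and the toxicity rule counts non-CNS events only from Grade 4. A Grade 3 allergic reaction after a completed scan therefore meets neither suspension rule.

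**The case against.** The text does not contradict itself, and a pooled limit is a legitimate choice. Five arguments deserve weight.

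- **The ceiling is rare.** A reader might infer from the boundary that four related deaths could readily pass. The deaths would have to be spread out (no more than 1 while 10-19 are enrolled, 2 while 20-29, 3 while 30-39), with no listed event in any other patient; even counting deaths alone the chance is 0.5-1.6%. By 40 enrolled, at most 3 enrolments remain. This stands.
- **Pooling makes the rule more sensitive.** Other listed events bring suspension forward, as Step 3 shows. This stands, and it is a reason to leave deaths in the count.
- **Deaths would not go unseen.** A reader might infer that only the twice-yearly reviews would notice them. Section 16.5.2 has toxicity monitored continuously, Section 10.5.2 requires 24-hour reports, Section 10.4.1 requires immediate reporting of serious events to the sponsor, and Section 10.4.3 sends unexpected serious reactions to the FDA and IRB. This stands as to awareness. None of these provisions suspends enrolment.
- **NSF is a different kind of event.** The plan says it has not been reported with normal renal function, so one case is a signal. Here the null hypothesis has 67% dead by 12 months (100% − 33%, Section 16.2), and possible attribution is a low bar. This weakens the analogy, but the attribution test excludes deaths judged unlikely or unrelated, and the consequence is a review.
- **A one-death trigger will fire often.** This stands and belongs in the stated cost.

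**Conclusion.** The point holds as a recommended change rather than an essential correction. The automatic rule does not suspend enrolment for a single related death at any stage, tolerates two to four as accrual grows, and is not in force before the tenth enrolment. Those boundaries are exact and need no assumption.

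The probabilities do rest on assumptions: related-death rates of 3-5%, immediate ascertainment and, for the pooled figures, other listed events in 5% of patients independently of death. On that basis the chance of at least one related death with no suspension by patient 43 is about 60% counting deaths alone and about 22-25% with pooling; for at least two it is 24-34% and about 8-10%. Late ascertainment would slow the rule, because a late event is set against a larger number enrolled.

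The documents do not support saying that several related deaths would probably pass without action, or that nobody would know of them. What is missing is an automatic step that pauses enrolment and takes each related death to the DSMB without waiting for the pooled limit or a scheduled review.

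**What to change.** In Section 16.5.2:

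1. Keep Grade 5 toxicity in the pooled more-than-10% count, so that the count loses no sensitivity.
2. Add one sentence: from the first patient, each Grade 5 event at least possibly related to treatment triggers the same suspend, examine and present-to-DSMB step as NSF. Retain the general reference to treatment. Naming only the tracer and radiotherapy could leave out a death attributed to temozolomide, which is part of protocol treatment under Section 7.3.
3. In the tracer rule, also count serious tracer-related allergic reactions first seen at the post-scan assessment, whether or not the PET was completed. The sponsor should choose and state the severity floor; without one, any Grade 1 reaction would count.

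The drafting cost is about two sentences. The operational cost should be stated openly: at assumed related-death rates of 2-5%, at least one pause by patient 43 is likely (58-89%), with about 1 to 2 expected. Each is a pause in enrolment for review. The sample size, the efficacy decision rule and the treatment of patients already enrolled are unchanged.
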